5.2.1.2. Safety Analysis Variables

Definitions of variables for safety analysis are listed by category and alphabetically within category.

Adverse event (AE)-related variables are listed below:

- **Adverse event (AE)** is defined as any untoward medical occurrence in a patient administered a pharmaceutical product, without regard to the possibility of a causal relationship.

AEs of special interest (AESIs)

AESI for olaratumab:

- Infusion-related reactions (IRRs)

AESI for doxorubicin:

- Cardiac arrhythmias
- Cardiac dysfunction

AESI for the combination of olaratumab and doxorubicin:

- IRRs
- Cardiac arrhythmias
- Cardiac dysfunction

Notes.

Categories of AESI may be modified as the understanding of the safety of the investigational drug increases. The final list of categories will be maintained at both compound and study level and reported in the CSR.

Consolidated AEs are composite AE terms consisting of synonymous PTs to allow meaningful interpretation of the AE data. Consolidated AE categories and PTs will be maintained at compound and/or study level and reported in the CSR.

Serious adverse event (SAE) is any AE that results in one of the following outcomes:

- death
- a life-threatening experience (that is, immediate risk of dying)
- persistent or significant disability/incapacity
- initial or prolonged in-patient hospitalization
- congenital anomaly/birth defect
- considered significant by the investigator for any other reason

Treatment-emergent adverse event (TEAE) is defined as an event that first occurred or worsened in severity after baseline and up to 30-day short-term follow-up visit.

Exposure-related variables are listed below:

- **Number of dose level reductions:** Sum of the number of dose level reductions as reported in the eCRF
- **Dose delays:** As reported in the eCRF
- **Dose withheld/skip (Not Administered):** As reported in the eCRF
- **Dose interruption(intravenous hold due to IRR):** As reported in the eCRF

Olaratumab or placebo treatment:

- Duration of treatment (weeks; 21 days added to duration of treatment because administration is every 3 weeks [on Days 1 and 8 of each 3-week cycle]) = $([\text{Date of last cycle Day 1} - \text{date of first dose}] + 21) \div 7$
- Cumulative dose, dose intensity, and relative dose intensity:
 - Cumulative dose (mg/kg) = Sum of (dose administered at each infusion [mg] \div Last available weight [kg])
 - Weekly dose intensity (mg/kg/week) = (Cumulative dose) \div (Duration of Treatment [week])
 - Planned weekly dose intensity (mg/kg/week) = $2 \times (20 \text{ mg/kg} + (\text{number of cycles} - 1) \times 15 \text{ mg/kg}) / (\text{number of cycles} \times 3 \text{ weeks})$
 - Relative dose intensity (%) = (Weekly dose intensity) \div (Planned weekly dose intensity) $\times 100$

Doxorubicin treatment:

- Duration of treatment (weeks) = $([\text{Date of last dose} - \text{date of first dose}] + 21) \div 7$
- Cumulative dose, dose intensity, relative dose intensity:
 - Cumulative dose (mg/m²) = Sum of (dose administered at each infusion [mg] \div Last available body surface area [BSA] [m²])
 - Weekly dose intensity (mg/kg/week) = (Cumulative dose) \div (Duration of treatment)
 - Planned weekly dose intensity (mg/m²/week) = $75 \text{ mg/m}^2 / 3 \text{ weeks} = 25 \text{ mg/m}^2/\text{week}$
 - Relative dose intensity (%) = (Weekly dose intensity) \div (Planned weekly dose intensity) $\times 100$

5.2.1.3. Patient-Reported Outcome Analysis Variables

Three scales will be used to assess patient reported Quality of Life (QoL) outcomes: EORTC-QLQ-C30, Modified Brief Pain Inventory – short form (mBPI-sf), and EQ-5D-5L.

EORTC-QLQ-C30

The European Organisation for Research and Treatment of Cancer Quality of Life Questionnaire Core 30 version 3.0 (EORTC-QLQ-C30), a self-administered, cancer-specific questionnaire consisting of 30 questions with multidimensional scales.

Assessments will be scored according to the EORTC QLQ-C30 Scoring Manual (Fayers et al., 2001). The 30 items (Q1-Q30) of the QLQ-C30 are scored to obtain 15 scales (1 global health status/QoL scale, 5 functional scales, and 9 symptom scales/items). A linear transformation is used to obtain scales ranging from 0 to 100 where:

- A high score for a functional scale represents a high / healthy level of functioning.

- A high score for the global health status / QoL represents a high QoL.
- A high score for a symptom scale / item represents a high level of symptomatology / problems.

EORTC QLQ-C30 (Version 3) Summary of Fifteen Scales and Scoring

Scale	Raw Score: Mean of items	Score
Global health status/QoL (QL2)	Q29, Q30	$\{1-(\text{Raw Score}-1)/6\} \times 100$
Functional scales		
Physical functioning (PF2)	Q1-Q5	
Role functioning (revised) (RF2)	Q6, Q7	
Emotional functioning (EF)	Q21 - Q24	$\{1-(\text{Raw Score}-1)/3\} \times 100$
Cognitive functioning (CF)	Q20, Q25	
Social functioning (SF)	Q26, Q27	
Symptom Scales		
Fatigue (FA)	Q10, Q12, Q18	
Nausea and vomiting (NV)	Q14, Q15	
Pain (PA)	Q9, Q19	
Dyspnoea (DY)	Q8	$\{(\text{Raw Score}-1)/3\} \times 100$
Insomnia (SL)	Q11	
Appetite loss (AP)	Q13	
Constipation (CO)	Q16	
Diarrhea (DI)	Q17	
Financial difficulties (FI)	Q28	

Worsening will be defined as an increase of at least 10 points for the symptom scales or a decrease of at least 10 points for the functional scales and the global health status/QoL scale. Time to worsening will be calculated as the time from the first study drug dose (baseline date) to the first observation of worsening. If worsening is observed after a missing value, it may be assumed that the worsening occurred at the time of the missing value. Otherwise, the patient may be considered lost to follow-up and censored at the date of last assessment. Patients with no post-baseline assessment will be censored at the baseline date. Patients who have the worst possible score at baseline or a missing baseline assessment (i.e. no assessment prior to or on the day of the first study drug dose) will not be included in this analysis. In addition, the following variables will be derived for each scale score:

- For each patient, change from baseline will be calculated for every postbaseline assessment by subtracting the baseline assessment result from the current assessment result.
- Maximum improvement and maximum worsening scores (over baseline) will be determined from the set of all postbaseline change scores.

- Maximum improvement and maximum worsening scores (over an assessment at start of monotherapy) will be determined from a set of change scores from 2nd monotherapy cycle onwards.
- A patient first improving over baseline by 10 points or more without prior worsening of 10 points or more will be categorized as having “improved” for that particular scale score during the study. A change of ≥ 10 points on the 100-point scales is considered clinically meaningful (Osoba et al. 1998)

Modified Brief Pain Inventory – short form (mBPI-sf)

The mBPI-sf assesses the severity of pain and its impact on functioning. The assessment will be analyzed primarily in terms of the “worst pain” score from each assessment. The first assessment will occur at Cycle 1 Day 1. **Time to first worsening of the mBPI-sf (Brief Pain Inventory Short Form Modified) “worst pain” score (TWP)** is defined for each patient as the time from the date of the first study drug dose (baseline date) to the first date of either a “worst pain” score increase of ≥ 2 points from baseline with no change in analgesic use or “worst pain” score increase of ≥ 1 point from baseline and an analgesic drug class increase of ≥ 1 level (Farrar et al., 2001; Rowbotham, 2001). If the patient has not worsened by either of these criteria, TWP will be censored for analysis on the last date the mBPI-sf was administered. Patients with a baseline worst pain score of 8 or more or with a missing baseline score (i.e. no assessment prior to or on the day of the first study drug dose) will not be included in the time to first worsening analysis.

A clinical pain response will be defined as a “worst pain” score decrease of ≥ 2 points from baseline with no change in analgesic use or a “worst pain” score decrease of ≥ 1 point from baseline and an analgesic use decrease of ≥ 1 level. Patients with a baseline worst pain score of 0 (best possible score) or with a missing baseline score will not be included in the analysis of this endpoint. The cumulative distribution of the percentage of pain responders by treatment arm as a function of time is to be presented graphically.

In addition to the TWP variable defined above, the following variables will be derived for the “worst pain” score:

- For each patient, change from baseline will be calculated for every postbaseline assessment by subtracting the baseline assessment result from the current assessment result.
- Maximum improvement and maximum worsening scores (over baseline) will be determined from the set of all postbaseline change scores.
- Maximum improvement and maximum worsening scores (over an assessment at start of monotherapy) will be determined from a set of change scores from 2nd monotherapy cycle onwards.
- A patient first improving over baseline by 2 points or more without prior worsening of 2 points or more will be categorized as having “improved” his/her score during the study.

EQ-5D-5L

The EQ-5D-5L responses may be incorporated into a cost-utility analyses. The EQ-5D-5L data will be scored as described in literature (van Hout et al. 2012). The index score is calculated

from a set of item weights to derive a score of 0 to 1, with 1 representing the best health status. United Kingdom (UK) weights will be applied for the base case (EuroQol, n.d). Geographic-specific weights will be used as appropriate and when available as part of the cost-utility analysis for that specific geography.

Each patient completing the EQ-5D-5L report the level, or score for each of 5 dimensions (mobility, self-care, usual activities, pain/discomfort, and anxiety/depression), as well as a visual analog scale (VAS) score. The index score is calculated as a function of individual levels (1=no problem, 2=slight, 3=moderate, 4=severe, and 5=extreme problem) from each of the 5 dimensions. The index score will not be computed for an assessment if the patient has 1 or more missing values among the 5 items. The VAS is a score reported by the patient ranging from 100 (best imaginable health state) to 0 (worst imaginable health state).

The analysis will include all cycles for which at least 25% of patients in each arm have an assessment. For cycles with data available from <25% of participants, analysis will be descriptive only.

The following variables will be derived for the EQ-5D-5L Index and VAS:

- For each patient, change from baseline will be calculated for every postbaseline assessment by subtracting the baseline assessment result from the current assessment result.
- Maximum improvement and maximum worsening scores (over baseline) will be determined from the set of all postbaseline change scores.
- Maximum improvement and maximum worsening scores (over an assessment at start of monotherapy) will be determined from a set of change scores from 2nd monotherapy cycle onwards.

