5.2. General Considerations

This document describes the statistical analyses planned prior to final treatment assignment unblinding of the aggregate database. Any change to the data analysis methods described in the protocol will require an amendment ONLY if it changes a principal feature of the protocol. Any other change to the data analysis methods described in the protocol and the justification for making the change will be described in the clinical study report (CSR). Additional exploratory analyses of the data will be conducted as deemed appropriate.

All tests of treatment effects will be conducted at a two-sided alpha level of 0.05 unless otherwise stated, and all confidence intervals (CIs) will be given at a two-sided 95% level, unless otherwise stated. Statistical analysis will be performed using SAS software (SAS, Version 9.1.2 or higher).

The following general terms will be used globally in the SAP:

- Unless otherwise specified, summary statistics stand for n, mean, standard deviation, median, minimum, and maximum for continuous variables; and frequency and percentage for categorical variables.
- **Study Treatment Period:** begins on the day the first dose of study treatment is administered and ends when the patient and the investigator agree that the patient will no longer continue study treatment. The date of this agreement is to be reported on the electronic case report form (eCRF) as the Date of Discontinuation from study treatment.
- **Postdiscontinuation Follow-Up:** begins the day after the patient and the investigator agree that the patient will no longer continue study treatment.

Short-term follow-up begins the day after the patient and the investigator agree that the patient will no longer continue study treatment and lasts approximately 30 days (± 7 days) (until the short-term 30-day safety follow-up visit is completed).

Long-term follow-up begins the day after short-term follow-up is completed and continues until the patient's death or overall study completion (whichever is earlier).

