5.7.1. Analysis Populations

Unless otherwise specified, all analyses will be based on the population of patients enrolled in the main protocol (Cohort 1). Patients enrolled under the extended enrollment addendum in Taiwan will be referred to as Cohort 2. Patients enrolled in Cohort 2 will not be included in the primary analysis of overall survival. As necessary, efficacy and safety analyses will be summarized for patients enrolled in Taiwan by pooling Cohort 1 and Cohort 2. All pooled analyses will be for descriptive purposes only.

[Table JGDJ.5.4](#) lists analysis population definitions and associated data type for analysis.

Table JGDJ.5.4. Analysis Populations

Population	Definition	Analysis Type / Variable	Note
Intention-to-treat (ITT) Population	All randomized patients	Baseline characteristics, concomitant medication, all efficacy analyses	Patients will be grouped according to randomized treatment.
Safety Population (SP)	All randomized patients who received any quantity of study drug	Safety, e.g. dosing/exposure, AE and resource utilization	Patients will be grouped according to treatment received as defined by the first dose received.
LMS subset of ITT Population	All randomized patients with LMS histologic subtype	Baseline characteristics, concomitant medication, all efficacy analyses	Patients will be grouped according to randomized treatment.

Abbreviations: AE = adverse event; ITT = intent-to-treat; LMS = leiomyosarcoma.

Compliance for the PRO instruments will be reported for the ITT population. All other PRO analyses will be on the ITT population and will include those from whom a completed PRO instrument was obtained at baseline and at least 1 postbaseline (either during study treatment period or 30-day postdiscontinuation follow-up period); thus, the actual patients included for each analysis will depend on the instrument and response variable.

A patient listing of analysis population details will be provided. This listing will be presented by treatment group and will include: investigator site, patient identifier, inclusion/exclusion flag for each population, and reason for exclusion from each population. All patients screened will appear on this listing.

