5.13. Patient-Reported Outcome Analyses

For each instrument, percentage compliance will be calculated as the number of completed assessments divided by the number of expected assessments (that is, patients still on study). Percentage compliance will be summarized by treatment group and overall. Similarly, the reasons for non-compliance will also be summarized descriptively.

Time-to-event variables will be analyzed using stratified log-rank tests (analogous to the primary analysis) for comparisons between study arms, stratified Cox models (for between-arm statistics including the treatment HR), and Kaplan-Meier method (for within-arm statistics).

Data will also be summarized descriptively for all of the variables identified Section 5.2.1.3, including shift tables.

QLQ-C30

Percentages of patients categorized as “improved” will be summarized and compared between study arms. Maximum improvement and worsening scores will be analyzed as continuous variables and compared between study arms using analysis of covariance (with both parametric and non-parametric p-values reported).

For the Physical functioning (PF2) as well as Emotional functioning (EF) scales, the change from baseline will be further analyzed by using mixed-effect repeated measures models based on restricted maximum likelihood estimation. Fixed effects in the model will include study treatment arm, baseline score, cycle number, and interaction term for study treatment arm and cycle number. The variance-covariance matrix that results in the minimum Akaike Information Criterion (Akaike 1973) from among unstructured, variance components, auto-regressive, and compound symmetric will be incorporated in the model. To implement the variance structure, patients will be included in the model as a random effect. The magnitude of the main effects and interactions will be evaluated and discussed. Based on the model-based means (LSMeans) from the repeated measures model, treatment group contrasts will be tested for each cycle number separately. Treatment group contrasts also will be tested for the treatment group marginal means.

Floor and ceiling effects will be summarized for each of the 15 scales. The presence of a significant ceiling effect suggests that not much improvement is possible for that scale. Likewise the presence of a floor effect suggests that worsening is less likely.

Modified Brief Pain Inventory – short form (mBPI-sf)

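### The between-arm comparison of QLQ-C30 and worst-pain 'improved' rates keeps patients in the denominator whose baseline score makes improvement impossible, which dilutes the rates and costs some power

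*SAP*

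**What the plan says.** SAP 5.2.1.3 derives an 'improved' category for each QLQ-C30 scale: "A patient first improving over baseline by 10 points or more without prior worsening of 10 points or more will be categorized" as improved. For the mBPI-sf worst-pain score it reads "A patient first improving over baseline by 2 points or more without prior worsening of 2 points or more will be categorized" in the same way. No baseline-score condition is attached to either variable.

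SAP 5.13 states, separately for the QLQ-C30 and the mBPI-sf, that the percentages improved "will be summarized and compared between study arms". It does not name the test. SAP 5.2 sets the default level: "All tests of treatment effects will be conducted at a two-sided alpha level of 0.05 unless otherwise stated".

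The PRO analysis set in SAP 5.7.1 is defined by form completion. The analyses "include those from whom a completed PRO instrument was obtained at baseline and at least 1 postbaseline". The section adds that the patients included will vary with the instrument and variable, but it presents this as a consequence of completion and states no room-to-improve rule.

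Neighbouring endpoints in 5.2.1.3 do carry baseline exclusions, each tied to its own analysis:
- QLQ-C30 time to worsening: "Patients who have the worst possible score at baseline or a missing baseline assessment" are left out.
- Time to worst-pain worsening: a baseline of 8 or more is left out.
- Clinical pain response: "Patients with a baseline worst pain score of 0 (best possible score) or with a missing baseline score will not be included".

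SAP 5.13 also plans a summary of floor and ceiling effects for the 15 QLQ-C30 scales and remarks: "The presence of a significant ceiling effect suggests that not much improvement is possible for that scale". That summary does not alter any denominator.

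**The concern.** A patient who cannot reach the threshold is certain to be counted as not improved, whichever treatment was given. Such patients carry no information about treatment. They lower both arms' rates and shrink the absolute difference.

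The SAP recognises the principle for the endpoints next to this one but does not carry it over. As a result, two responder-type pain measures, defined in the same section and compared in the same paragraph of 5.13, would have different denominators with no stated reason. PROs are a listed secondary objective, so these percentages are likely to be reported. A reader of a low 'improved' rate could not tell from the rate itself how much of it reflects patients who had nothing to gain.

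**Working it through.** **No planned figure to reproduce.** The documents give no improvement rate, ceiling share or power for 'improved'.

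**Step 1: which baselines make improvement impossible.** From the scoring table in SAP 5.2.1.3, the step between adjacent scores is 100 / (number of items x divisor in the scoring formula).

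| Scale | Step | Baselines that cannot improve by 10 |
|---|---|---|
| Physical functioning (5 items, divisor 3) | 100/15 = 6.7 | 93.3, 100 |
| Emotional functioning (4 items, divisor 3) | 100/12 = 8.3 | 91.7, 100 |
| Global health status (2 items, divisor 6) | 100/12 = 8.3 | 91.7, 100 |
| Role, cognitive, social functioning (2 items, divisor 3) | 100/6 = 16.7 | 100 |
| Fatigue (3 items, divisor 3) | 100/9 = 11.1 | 0 |
| Other symptom scales (1 or 2 items, divisor 3) | 33.3 or 16.7 | 0 |

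Worst pain is scored 0-10 in whole points, so a fall of 2 is impossible from 0 or 1.

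**Step 2: effect on the rates.** Let c be the share of patients at ceiling, and p0 and p1 the control and olaratumab improvement rates among the others. With everyone counted, the rates are p0(1-c) and p1(1-c):
- The absolute difference becomes (p1-p0)(1-c).
- The ratio p1/p0 does not change.

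Example with assumed values p0 = 30%, p1 = 43%, c = 30%: the rates become 21.0% and 30.1%, and the difference falls from 13 to 9.1 points.

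**Step 3: effect on power.** Inputs: two-sided 0.05 (SAP 5.2) and 230 per arm (SAP 5.1), which is an upper bound for the PRO set. The test is a two-proportion z-test with pooled null variance:
- Everyone counted: rates p(1-c) on n = 230.
- Restricted: rates p on n = 230(1-c).

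The relative efficiency of counting everyone is (1-pbar)/(1-pbar(1-c)), where pbar = (p0+p1)/2. This is below 1 whenever c > 0. In the example, pbar = 0.365 and the efficiency is 0.635/(1 - 0.2555) = 0.853.

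| p0 v p1 (assumed) | c (assumed) | Power, everyone | Power, restricted |
|---|---|---|---|
| 15% v 25% | 10% | 71.1% | 72.2% |
| 15% v 25% | 30% | 58.1% | 61.2% |
| 20% v 32% | 30% | 64.7% | 69.1% |
| 30% v 43% | 10% | 76.3% | 78.7% |
| 30% v 43% | 30% | 61.0% | 68.0% |
| 30% v 43% | 50% | 43.8% | 53.5% |
| 60% v 73% | 30% | 49.9% | 69.7% |
| 60% v 73% | 50% | 31.5% | 55.2% |

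With 200 per arm, 40% v 55% and half at ceiling, the reported rates are 20% v 27.5%, and power is 42% against 57%.

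**Step 4: check on error rate.** A simulation of 200,000 trials with random ceiling status, c = 30% and no treatment effect (30% in both arms) gave type I error of 4.96% with everyone counted and 4.94% restricted. With 30% v 43%, power was 61.4% and 68.3%, in line with the formula.

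**The case against.** The strongest reply is that this is a question of estimand. The proportion improved among all patients with forms is a legitimate population rate, and restricting to patients with room to improve answers a different question. That stands, and it is why the all-patient rate should be kept alongside.

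Second, the SAP is not blind to the issue. The planned ceiling-effect summary and shift tables would help a reader interpret the QLQ-C30 rates. For pain, clinical pain response already leaves out baseline 0 and is itself compared between arms. Both deserve credit. Neither changes the 'improved' denominator, the ceiling summary does not cover pain, and excluding only 0 would still leave baseline 1, from which a 2-point fall is impossible.

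Third, SAP 5.6 places these comparisons outside the alpha-controlled family, and no power is claimed for them. This limits the weight of the point.

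Fourth, SAP 5.3 stratifies PRO analyses by three factors, which Protocol 12.2.6 counts as 16 strata. With half at ceiling, 115 per arm over 16 strata averages about 7 per arm per stratum, against about 14 for 230. The power figures above are unstratified and do not count that cost.

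A reader might infer that the rates would mostly reflect how many patients had a problem at baseline. The documents do not support this: they give neither factor of the product. Eligibility at ECOG 0-1 makes ceiling scores plausible but does not establish them, since ECOG 1 already means some restriction (Protocol Attachment 4).

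**Conclusion.** The gap is real and minor. Patients who cannot meet the threshold are counted as not improved in a planned between-arm comparison, although the SAP applies comparable exclusions to adjacent endpoints.

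A reader might infer bias between the arms or an inflated error rate. Neither follows. Ceiling status is fixed at baseline, type I error holds and the relative risk is unchanged. The rates are low only relative to patients who could improve.

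The size rests wholly on assumed values. With 10-50% at ceiling, improvement rates of 15-43% among the others and 230 per arm, the loss is about 1 to 10 percentage points of power. At 60% v 73% it reaches about 24 points with half at ceiling. Real PRO denominators will be below 230, and the share at ceiling will differ by scale.

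The QLQ-C30 worsening exclusion has a similar gap: patients one step above the worst score on physical functioning (6.7), emotional functioning or global health status (8.3) cannot lose 10 points but remain at risk. This is likely to involve very few patients, and no material effect should be claimed.

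**What to change.** In SAP 5.2.1.3, state that the between-arm comparison of 'improved' is made in patients whose baseline is at least 10 points from the best possible score on that QLQ-C30 scale, or whose baseline worst pain is at least 2. Keep the all-patient rate as a sensitivity analysis, and report the number excluded by arm for each scale. Set the rule before the sponsor is unblinded, so that the denominator is not a post hoc choice.

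Optionally, extend the QLQ-C30 time-to-worsening exclusion to patients less than 10 points from the worst score.

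The cost is a few lines of SAP text and a baseline filter. The filter uses baseline data only, so it adds no bias beyond what the existing requirement of a postbaseline form may bring. The drawbacks are that the evaluable number will differ by scale and the strata become sparser, so the SAP should also name the test and say how sparse strata are handled.

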12.2.10. Analyses of Patient-Reported Outcomes (PROs)

Patient-reported outcomes are measured through the following:

- mBPI-sf (Brief Pain Inventory [Short Form] Modified)
- EORTC QLQ-C30 (The European Organization for Research and Treatment of Cancer Quality of Life Questionnaire Core 30)
- EQ-5D-5L (EuroQol 5-Dimension 5-Level)

For each instrument (mBPI-sf, EORTC QLQ-C30, and EQ-5D-5L), percentage compliance will be calculated as the number of completed assessments divided by the number of expected assessments (that is, patients still on study and alive). Percentage compliance and reasons for non-compliance will be summarized by treatment arm and time point.

Data will be separately summarized by treatment and time point using descriptive statistics. The main efficacy measure for the pain endpoint will be the time to first worsening of the mBPI-sf “worst pain” score. Time to first worsening in pain will be described using the method of Kaplan and Meier and analyses will be made between the 2 arms by a log-rank test. “Worsening” will be defined as either a “worst pain” increase of ≥ 2 points postbaseline (Farrar et al. 2001; Rowbotham 2001) or an analgesic drug class increase of ≥ 1 level. However, other approaches to defining clinically meaningful worsening in pain might be considered. Further details will be provided in the SAP.

Additionally, time to first worsening of QLQ-C30 scale scores (see Section 10.2) will be analyzed using Kaplan-Meier and Cox methods. Further statistical analysis to be performed for PROs will be defined and detailed in the SAP.

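### The SAP defines worst-pain worsening more narrowly than the protocol, without a stated reason, so a rise of 2 points or more with an analgesic step-down is not an event

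*SAP*

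**What the plan says.** Protocol 12.2.10 makes time to first worsening of the mBPI-sf worst-pain score the main efficacy measure for pain, compared between arms by log-rank test. Worsening is a rise of at least 2 "points postbaseline" "or an analgesic drug class increase of" at least 1 level. The section then says that other definitions might be considered and that the SAP will give details.

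SAP 5.2.1.3 has two limbs:

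- a rise of at least 2 "points from baseline with no change in analgesic use"; or
- a rise of at least 1 "point from baseline and an analgesic drug class increase of" at least 1 level.

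For everyone else: "If the patient has not worsened by either of these criteria, TWP will be censored for analysis on the last date the mBPI-sf was administered".

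On baseline scores, the SAP leaves out of this analysis "Patients with a baseline worst pain score of 8 or more or with a missing baseline score". Protocol 10.2.1 sets the same cut-off of 8. For the QLQ-C30 time-to-worsening analyses the SAP is less restrictive. Apart from missing baselines, it leaves out only "Patients who have the worst possible score at baseline".

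**The concern.** One endpoint has two event definitions. The SAP turns the protocol's stand-alone analgesic criterion into a joint one and attaches an analgesic condition to the 2-point criterion. A patient whose score rises by 2 or more while the analgesic class goes down meets neither limb. That patient stays event-free and is censored at the last questionnaire unless a later assessment qualifies, in which case the event is dated late. A large recorded rise in pain is then handled as no worsening on the main pain measure.

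The SAP gives no reason. Its revision history says only that details for patient-reported outcomes were added, and both documents cite the same two pain publications for different rules. SAP 5.13 names no sensitivity analysis on the protocol definition, so a reader of the results could not see whether the choice of rule mattered.

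The baseline cut-off is a separate, smaller matter. It removes patients with severe pain who could still worsen under the rule in use.

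**Working it through.** The documents give no event count, power or effect size for this endpoint, so there is no figure to reproduce. The check is logical.

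**Inputs.** Score range 0 to 10 and six analgesic categories, coded 0 to 5 (Protocol 10.2.1 and Table JGDJ.5); protocol rule (Protocol 12.2.10); SAP rule (SAP 5.2.1.3). Let d be the score change and a the change in analgesic level.

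- Protocol event: d ≥ 2 or a ≥ 1.
- SAP event: (d ≥ 2 and a = 0) or (d ≥ 1 and a ≥ 1).

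**By level, 9 states.**

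| Score change | Class down | Class same | Class up |
|---|---|---|---|
| 0 or lower | neither | neither | protocol only |
| +1 | neither | neither | both |
| +2 or more | protocol only | both | both |

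The protocol counts 5 states and the SAP 3. No state is an event under the SAP alone.

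**Full enumeration, baselines 0 to 7.** There are 8 × 11 = 88 baseline/follow-up score pairs and 6 × 6 = 36 pairs of analgesic codes (6 same, 15 up, 15 down), giving 88 × 36 = 3168 states. Of the 88 score pairs, 9 + 8 + … + 2 = 44 have d ≥ 2 and 10 + 9 + … + 3 = 52 have d ≥ 1.

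- SAP: 44 × 6 + 52 × 15 = 264 + 780 = 1044.
- Protocol: 44 × 36 + (88 − 44) × 15 = 1584 + 660 = 2244.
- Difference: 2244 − 1044 = 1200. This is 44 × 15 = 660 (rise of 2 or more, class down) plus (88 − 52) × 15 = 540 (no rise, class up).

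The SAP rule is strictly narrower. These are counts of logical states, not patient frequencies.

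**Same-class switches.** Codeine and oxycodone share code 2. If the SAP's condition on analgesic use covers any drug change, a rise of 2 or more with such a switch fails limb 1 for the change and limb 2 for want of a class increase. Protocol 10.2.1 supports that reading, since it describes changes in use as new or stopped analgesics. The SAP's own pain-response rule points the other way, because it expresses a decrease in analgesic use in levels. The text does not settle it.

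**Baselines of 8 or more under the SAP rule.**

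| Baseline | Class same | Class up | Class down |
|---|---|---|---|
| 8 | 10 qualifies | 9 or 10 qualifies | none |
| 9 | none | 10 qualifies | none |
| 10 | none | none | none |

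On the score alone, only 10 makes the SAP rule impossible to meet. Under the protocol rule even a baseline of 10 can worsen through a class increase.

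**The case against.** The strongest reply is that the protocol delegated this choice. Section 12.2.10 allows other approaches and section 10.1.4 leaves event and censoring definitions to the SAP. A reader might infer that the SAP breaches the protocol; the documents do not support that. What remains is that Protocol 12.2.1 expects modifications made in the SAP to be described and justified, and this one is not justified.

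A reader might also infer that analgesic escalation generally hides worsening. It does not. A rise of 2 or more with a class increase counts through the second limb, as does a 1-point rise with a class increase. Only escalation without a score rise is missed. Requiring some rise is defensible for an endpoint named after the score, so that state calls for a sensitivity analysis and need not change the main rule.

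A count that treats same-class switches as a separate failing state gives 6 against 3 of 12 and might suggest that half the worsening is lost. It depends on one reading of the analgesic condition, and no count of states measures lost events.

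The cut-off of 8 might look like a SAP departure that removes the patients with most pain from the pain results. It is the protocol's own rule, and the SAP applies it only to the time-to-first-worsening analysis. SAP 5.13 also plans repeated-measures models of the pain items and a comparison of maximum worsening. The QLQ-C30 pain scale has its own time-to-worsening analysis with no analgesic condition.

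**Conclusion.** The concern holds as an unexplained narrowing of the event definition: 3 of 9 states against the protocol's 5, with every SAP event also a protocol event. The clear misclassification is the rise of 2 or more with a step-down, which is lost however the analgesic condition is read. The loss of same-class switches depends on the literal reading. A class increase without a score rise is worsening only by the protocol's definition.

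The baseline cut-off is a mismatch shared by both documents. For a score of 9 it matters only through the joint limb.

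The share of patients affected cannot be derived, since neither document gives a distribution of baseline pain or analgesic change. Nor can the direction of any effect on the comparison between arms. Pain is a secondary objective, and SAP 5.6 limits error control to OS, PFS and ORR, which do not depend on this rule. The point is worth correcting, but it does not bear on the trial's primary conclusions.

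**What to change.** Before the sponsor is unblinded, amend SAP 5.2.1.3 as follows:

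1. Count any rise of 2 points or more as worsening, whatever the analgesic change, and keep the limb of at least 1 point with a class increase. This makes 4 of the 9 states events and settles the same-class question for worsening.
2. Add the protocol definition (2 points or more, or a class increase alone) as a named sensitivity analysis, and give the reason for the main rule.
3. Add a sensitivity analysis on baseline that leaves out only patients who cannot meet the rule in use. On the score alone that is 10 under the SAP rule. It should not be carried over to the protocol rule, where a patient at 10 can worsen by class increase. If the main cut-off of 8 is changed, reconcile Protocol 10.2.1 as well.

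Scores and analgesic use are already collected, so items 1 and 2 cost SAP wording and programming. The downside is some additional events that may reflect analgesic changes. Showing the definitions side by side lets the reader judge that.
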